## Assessments

Participants' assessments will be conducted at baseline, 6, and 12 months of the intervention. The following table and cited references describe the surveys and measurements conducted at each time point:

Instrument	BL	6 mo	12 mo
Demographic, social support and potential mediators/moderators			
Demographic and socioeconomic status			
Demographic variables	X		
Socioeconomic status variables, use of nutrition assistance programs, environmental changes	X	X	X
Current medications	X	X	X
Social support provision, receipt and enjoyment			
Number of times a person completes a social support-related activity (SS provision)		X	X
Adapted Multidimensional Scale of Perceived Social Support Scale (MSPSS) – (SS perceived) 		X	X
Ratings each participant gives to the social support provided to them after they request support (SS perceived)		X	X
Total number of times other participants provided support to the individual (SS receipt)		X	X
EGameFlow (enjoyment) 		X	X
User engagement and user burden			
User Engagement Survey* (adaptation) 	X	X	X
User Burden Scale* (adaptation) 	X	X	X
Self-efficacy and -regulation and motivation			
Weight Efficacy Life-Style Questionnaire (WEL-Q) 	X	X	X
Treatment Self-Regulation Questionnaire (TSRQ) 	X	X	X
Potential drivers of weight loss			
NCI's Automated Self-Administered 24-hour Dietary Recall (ASA24®) – 3 unannounced recalls – two weekdays, one weekend day) 	X	X	X

Physical Activity (FitBit tracker) – minutes per week of MVPA (min:10h/d, 3 valid days) 	X	X	X
Exercise Vital Sign Questionnaire 	X	X	X
The Stanford Leisure-Time Activity Categorical Item (L-Cat), short version 	X	X	X
Physiological and anthropometric measures			
Height (self-report) / weight (FitBit Aria Scale) 	X	X	X
Hip and Waist circumference (self-report).	X	X	X
T2DM (Type 2 Diabetes Mellitus) risk factors (risk score 0 – 10)	X	X	X
Self-monitoring adherence and study compliance/responsiveness			
Monthly survey (self-monitoring)		X	X
Adherence to FitBit devices usage (mLife app – rewards or points)		X	X
Adherence to self-monitoring diet (mLife app - logging $\geq 2$ eating occasions per day)		X	X
Use of intervention components (mLife app - use of all intervention components)		X	X
Factors that may affect compliance: differential dropouts and reasons to discontinue the study		X	X

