## Intervention components procedures

Both groups will receive the same intervention, but to isolate the impact of points/social gaming, the mLIFE+points group will receive points for engaging in social support-related behaviors, and the mLIFE will not. The intervention components and points system is displayed below.

Intervention Components	Points
Podcasts (within the app):	
Nutrition and exercise information	N/A*
Audio diary	N/A
Goal setting	N/A
mLIFE app:	
Self-regulation features	
Diet, PA**, and weight tracking app components	N/A
App notifications at specific times to remind participants to self-monitor	N/A

Newsfeed of activity listing when someone self-monitored diet, PA, and weight; downloaded a podcast or read a tip of the day; or requested social support on a topic.	N/A
Leaderboard and Points tracker	N/A
Social support features	
Thumbs Up that someone tracked their diet for the day (posted to newsfeed)	1
Thumbs Up a notification that someone logged 30 min of PA for the day (posted to newsfeed)	1
Thumbs Up a notification that someone logged their weight for the day (posted to newsfeed)	1
Thumbs Up a notification that someone listened to a podcast or read a tip of the day (posted to newsfeed)	1
Sending someone an encouraging message when they have not logged on (choice of 3 pre-populated messages or ability write their own message)	1
Sending out a request for help on a specific topic related to diet or PA	1
Responding to a request for help	1
Thanking someone for a thumbs up or response to a request for help (participants will also rate how supported they felt for each response they receive)	1
Total max points possible per day:	8

Within the study's app, the participants can monitor their physical activity data from the FitBit tracker, log their food and engage in social support activities. FitBit app is used for body weight saving and in cohort 2 only, Fitbit nutrition feature is used for diet logging. The procedures for the 5 components are described below

---

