## Social support activities and gamification

The mLife app offered eight social support activities to engage users and test gamification. It automatically posted newsfeed when users logged meals, exercised, tracked weight, or listened to podcasts. Users could “like” posts and request support from peers by commenting or asking questions. Peers could comment and respond to support requests, and users received notifications when peers offered support. Refer to the graph below that shows the gamified social actions within the application id and point value for the leaderboard.

[figure not shown]

Id	Name	Point Value
3	Respond to a support request*	1
4	Outreach	1
5	Thank for thumbs up/Comment*	1
6	Request support	1
7	Thumbs up logged weight	1
8	Thumbs up logged diet	1
9	Thumbs up logged physical activity	1
10	THUMBS UP READ TIP OF THE DAY OR LISTENED TO A... 	1
12	Reply to a Comment	0

Participants are also prompted to send supportive messages to inactive peers. When inactive for more than 24 hours, an outreach request is posted in the newsfeed: “(username) hasn’t been active for more than a day. Please send them an encouraging message to return.” Participants can choose a pre-written message or create a custom message and send it via text. Pre-written messages are created using Social Cognitive Theory to target social support, self-efficacy, and outcome expectations regarding self-monitoring behavior. Once an outreach message is sent, the request is closed.

Participants earn up to 8 points per day for social support interactions. They can provide support as many times as desired, with a maximum of 1 point per activity. The mLife+Points group views the 8 activities, their daily points, and an overall leaderboard that resets monthly to boost motivation. The mLife group is unable to see the points earned; they have daily checklists. However, the mLife app calculates points for objective comparison between groups.

Posting a “request for support” comment or question in the app’s newsfeed allows mLife peers to comment and respond. Initially, participants could only post one response to peer requests to control moderation, but this limited social interactions, so unlimited responses were allowed at the 8 weeks data inspection. See the comment replies example graph below.

All participants' social interactions are posted in the newsfeed.

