## **Analysis Plan**

### **I. Below details how the outcomes will address the hypotheses being tested:**

We have two main hypotheses in this study. We are examining our outcomes among 240 adults with overweight or obesity and  $\geq 3$  T2DM risk factors.

Hypothesis 1: That the SocialPOD+points group will lose significantly more weight than the SocialPOD-points group.

Hypothesis 2: That the SocialPOD+points group will have greater objectively measured levels of social support provision and receipt than the SocialPOD- group

In order to ensure that each of these hypotheses can be addressed we must measure the following outcomes:

Objective body weight assessments

Objective assessment of social support provision and receipt via the app

Type 2 diabetes risk factors (assessed at baseline, 6 months, and 12 months): body weight, body circumference measures, and blood pressure

Demographic data (race/ethnic group and sex)

These outcomes will help us examine how weight loss and social support provision and receipt may differ between groups.

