### **III. Below describes our plans for interim and final analyses and methods for handling missing data:**

#### ***Aims 1 and 2***

Data from all study measures will undergo initial data cleaning to identify potential outliers, determine distributions of variables, assess normality, and enumerate loss to follow-up and other missing data. Descriptive statistics at baseline will be compared between treatment groups to evaluate the success of randomization. ***Analyzing changes in weight between groups at year one***

***(Primary Aims 1):*** For Aim 1, the two levels of the treatment effect will be assignment to SocialPOD+points vs. SocialPOD-points, and the entire study sample will be included. Primary Aim 1 will be addressed using a repeated-measures mixed model with maximum likelihood estimation as provided by PROC MIXED in the SAS® system. Under the assumption that missing data are missing at random, mixed models provide unbiased estimates. These will be adjusted using robust computation of standard errors if non-normality is detected. These models will be estimated applying an intent-to-treat principle. Models for each primary aim are of the same form, with the difference of the groups being compared. Models will examine weight at baseline and at 12 months with a two-level time effect, two-level treatment effect, and two-way interaction between time and treatment. The repeated-measures model will contain time, treatment, time-by-treatment interactions, and any covariates associated with weight loss. Models will be adjusted for changes in PA (via

accelerometers). If the time-by-treatment interaction in a model is significant at the 0.05 level, this will be interpreted as a significant weight-loss effect for one treatment relative to the other.

**Analyzing differences in social support provision and receipt between groups (Aim 2):** For Aim 2, the model will regress support provided (total points earned) and social support received (mean of ratings of support provided to the individual over the 12 months) on treatment group, adjusted for the same covariates used in Aim 1.

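### Aim 2 'support received' is a mean of ratings that exists only for participants who asked, were answered and rated, so the arms may be compared on subsets formed after randomisation

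*Combined protocol and SAP*

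**What the plan says.** The Aim 2 paragraph in part III of the Analysis Plan has two outcomes. Provision is total points earned. Receipt is the second regression: "social support received (mean of ratings of support provided to the individual over the 12 months) on treatment group". It is the only receipt outcome named in the model.

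Two places define when a rating comes into being. The Assessments table lists "Ratings each participant gives to the social support provided to them after they request support (SS perceived") as one of its measures. The points table under Intervention components procedures, in the row for thanking a peer, adds that "participants will also rate how supported they felt for each response they receive".

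The same points table gives one point each for "Sending out a request for help on a specific topic related to diet or PA", for "Responding to a request for help" and for the thanking row. The section Social support activities and gamification shows the points to one arm only: "The mLife group is unable to see the points earned; they have daily checklists".

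The Assessments table labels a different measure as receipt: "Total number of times other participants provided support to the individual (SS receipt"). Hypothesis 2 in part I of the Analysis Plan concerns "greater objectively measured levels of social support provision and receipt". Aim 2 is listed among the primary aims in the synopsis, where its hypothesis also covers perceived support.

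**The concern.** A per-person mean rating is undefined for someone who never asked, got no reply or did not rate. The plan does not say how such people are analysed. An ordinary regression would leave them out, so the result would describe raters rather than everyone randomised.

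This would be a loss of precision only, if having a rating were unrelated to arm or to how supported people feel. Here the intervention under test rewards the very steps that create a rating. If points work as intended, more mLife+points participants may enter the rated set, and they may differ from control raters in how supported they felt to begin with. The same applies within the mean: it gives one person's single rating the same weight as another person's many, and the number also depends on behaviour after randomisation.

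At stake is the receipt half of a primary aim. A difference in mean ratings, or its absence, could reflect who chose to ask as well as what points do. Weight (Aim 1) and points earned (the provision half of Aim 2) are not touched.

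**Working it through.** **1. The plan's own Aim 2 figure.** Statistical Design and Power assumes a difference of 50 points with SD 105 and states 95% power for points earned. Standardised difference: 50/105 = 0.476. With 120 per arm, two-sided alpha 0.05 (sidedness is not stated; two-sided assumed) and a normal approximation:

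- 0.476 × √(120/2) = 3.689; power = Φ(3.689 − 1.96) = 0.958.

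The stated figure reproduces at the full 240. At 100 per arm, the number before the attrition inflation, it is Φ(3.367 − 1.96) = 0.920. No power is stated for the ratings outcome.

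**2. When the outcome exists.**

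| Step needed for a rating | Earns a point | Points visible to |
|---|---|---|
| Participant requests support | yes | mLife+points only |
| A peer responds | yes | mLife+points only |
| Participant rates (thanking row) | yes | mLife+points only |

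The count of times others gave support needs none of these from the recipient. It takes the value zero for someone who received nothing.

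**3. Illustration of bias with no true effect.** All inputs here are assumptions; the documents give neither the share with a rating nor any correlation. Let felt support be standard normal, and let r be its correlation with a latent tendency to have a rating. If a proportion p of an arm has a rating, the mean among raters is r·λ(p), where λ(p) = φ(z_p)/p and z_p is the normal quantile of p.

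- λ(0.7) = 0.497; λ(0.5) = 0.798; difference, points minus control = −0.301.
- r = 0.3: 0.3 × (−0.301) = −0.09 SD. r = 0.5: 0.5 × (−0.301) = −0.15 SD.
- r = −0.3 or −0.5: +0.09 or +0.15 SD. r = 0: zero.
- Equal shares (for example 90% in both arms): zero for any r.

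Other assumed shares:

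| Rated, points / control | r = 0.3 | r = 0.5 |
|---|---|---|
| 90% / 70% | −0.09 SD | −0.15 SD |
| 70% / 50% | −0.09 SD | −0.15 SD |
| 80% / 50% | −0.13 SD | −0.22 SD |
| 80% / 40% | −0.19 SD | −0.31 SD |

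Reversing the sign of r, or giving controls the larger share, reverses every sign in the table.

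**4. What this does to the test, at 70% / 50% of 120 per arm.** Raters: 84 + 60 = 144 of 240, so 96 (40%) have no value. The variance among raters is 1 − r²λ(λ + z_p). For r = 0.3 this is 0.954 and 0.943; the standard error is √(0.954/84 + 0.943/60) = 0.165; the shift is 0.090/0.165 = 0.55 standard errors, and the two-sided type I error is 0.085. For r = 0.5 the same steps give 0.161. If the 0.476 effect size carried over to ratings, which the documents do not claim, power would be Φ(0.476/√(1/84 + 1/60) − 1.96) = 0.804.

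**The case against.** Three points deserve weight.

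*Few people may lack a rating.* The training agenda, used for both arms, has attendees practise making a request, rating a reply, or both. The mean runs over 12 months, so one rating at any time is enough. Controls also have daily checklists covering the activities, so both arms are prompted. This stands, and it is why no rated share can be asserted. It does not close the gap. The agenda allows a request without a rating, a request may go unanswered, and a single practice rating would then serve as that person's 12-month score.

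*The plan may already cover it.* Part III is headed as dealing with missing data for both aims and refers to mixed models, missing at random and intention to treat. Those sentences sit in the Aim 1 repeated-measures text. The Aim 2 model has one value per person, and someone without a value adds nothing to it. The shared covariates do not model who rates; one of them, change in physical activity, is itself measured after randomisation.

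*The figures are invented.* They are, and they are labelled so. A reader might infer from them that 40% of participants will be dropped, or that points will look harmful. The documents support neither: they give no share of raters and no correlation, and they do not state that non-raters are excluded.

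**Conclusion.** The concern holds as a fault in how the outcome is defined. As written, the receipt outcome does not exist for every randomised participant. Its existence depends on behaviour that the points reward in one arm, and no text says what happens to people without it. The comparison may therefore not be of the randomised groups.

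How much this matters cannot be fixed from the documents. Under the assumed 70% versus 50% and a correlation of 0.3 to 0.5 in absolute value, the shift is 0.09 to 0.15 SD in either direction, with type I error of 0.085 to 0.161 instead of 0.05. It is nil if the shares match and raters are selected alike in both arms, or if rating is unrelated to felt support. It would be going too far to say that treatment is known to change who is analysed, or that the bias runs against mLife+points.

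The sections also disagree on the construct: the model calls the ratings received support, the Assessments table calls them perceived support, and Hypothesis 2 asks for objective measurement.

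**What to change.** In the Aim 2 paragraph of the Analysis Plan:

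1. Make the receipt outcome the app count already labelled as receipt in the Assessments table, with zero allowed. This matches Hypothesis 2.
2. Analyse the adapted MSPSS at 12 months as the perceived-support outcome. It is already collected, does not depend on having made a request, and serves the perceived part of the Aim 2 hypothesis. It should not stand in for receipt, since that would leave objectively measured receipt without an endpoint.
3. Report mean ratings descriptively among raters, with the number and percentage of raters in each arm.
4. State how missing data are handled for each outcome.

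The cost is a change of wording; no new data are needed. There are small downsides. The count measures how much support arrived, not how it felt, and it stops accruing when an account is inactivated after withdrawal or exclusion. The MSPSS is subject to survey non-response and has no baseline value in the Assessments table, so its missing-data approach cannot rest on a baseline score and must be spelled out.

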#### IV. Below details various types of bias and how our study aims to avoid them.

Type of Bias	How to Avoid
Pre-trial bias	
Flawed study design	We have a clearly defined risk and outcome and are using objective or validated methods. Standard operating procedures will be developed for data collection and assessors will be blinded to random assignment.
Selection bias	We will select participants using rigorous criteria to avoid confounding results. Participants will originate from the same general population. Because this is a well-designed, prospective study, selection bias should be avoided as outcome is unknown at time of enrollment.
Channeling bias	We will assign participants to study cohorts using rigorous criteria, stratifying by sex and race.
Bias during trial	
Interventionist bias	All study personnel interactions with participants will be standardized. As part of our treatment fidelity process, interactions with participants (e-mails, phone calls, etc.) will be regularly assessed and monitored to assure equal treatment among groups.
Recall bias	We will use objective data sources whenever possible. While surveys and the dietary recalls will rely on memory, these measures are currently the gold-standard way to assess these outcomes.
Transfer bias	We will carefully design plan for lost-to-follow-up participants prior to the start of the study. This will include number of contacts required after a participant does not attend classes or assessment visits.

Outcome Misclassification	We are using objective validated measures to assess all primary outcomes.
Bias after trial	
Citation bias	Our trial will be registered with clinicaltrials.gov prior to study recruitment for cohort 1. We will check registries for similar unpublished or in-progress trials prior to publication.
Confounding	Known confounders will be controlled during data analysis (such as medications). Unknown confounders will be controlled with randomization.

\* Adapted from Pannucci CJ, Wilkins EG. *Plast Reconstr Surg.* 2010 Aug; 126(2): 619–625.

## V. Consideration of relevant biological variables

Of primary interest in the present study will be examining differences in outcomes by sex and age. Previous research has demonstrated that men lose more weight than women in behavioral weight loss interventions, but there is no indication that different weight loss strategies should be used. There is evidence that men may interact with technology, including health-related mobile technology, differently than women. For example, a study examining gender differences in usage of a physical activity app found that enjoyment and goal-setting were more important for women than men but that men more often shared their results and used the live tracking function in the app. Other research has found that men feel that mobile phone usage is more appropriate across a variety of social situations than women. In addition, those under 50 (and particularly those under 30) tend to have higher rates of smartphone ownership than those over 50. Based on these findings, we aim to conduct sub-analyses examining the impact of sex and age on social support provision and receipt and weight loss. We have been successful recruiting both men and AA participants in our previous studies and being situated in South Carolina and housing this work within the Prevention Research Center (where the current main research project is among AA churches in SC) will ensure we can consider both of these relevant biological variables. Our models will also control for other factors that could impact outcomes, including age, BMI, SES, baseline lab values, and medication use.

**A. Below details our approach to data management and validation, including our data management system, methods of data entry and cleaning, and event tracking and logistics**  
 [name], Project Manager, and [name], study PI, will develop and maintain the computerized data management system for this study. Use of the data management system will be restricted to only those persons having access authority.

### ***Participant surveys***

Participants will complete all surveys electronically using a secured online platform. Electronic data will be imported into the study's database. Any paper documents, like attendance sheets, will be entered in the tracking database and stored in a locked filing cabinet. This study will use the IRB-approved OneDrive for storage of online files.

### ***Local Tracking Application***

An online tracking database will be used to track study participants. This local application will allow the study personnel to input demographic, contact information, form & visit tracking, and other data about individual participants. Access to the local application will be restricted by use of individual username and passwords.

The tracking database will have three primary forms:

Screening Forms – This form is used to track attempts to reach participants who completed an online screening form.

Measurement Tracking – This form tracks all measurement activities, including scheduled and actual dates of all measurement visits; location of measurement visits; return of accelerometers; distribution of incentives; completion of the three ASA24 dietary recalls; and participant status and status changes.

Intervention Tracking – This form has subforms that are used to record randomization assignment; participant-level tracking for the intervention groups.

Below is a screenshot of the tracking application we are currently using in our NIH R01 study:

